Metacognitive strategy training (MCST), specifically the Cognitive Orientation to daily Occupational Performance (CO-OP) approach, is a potential solution to address both of these gaps. CO-OP is a performance-based, problem-solving approach that enables participants to improve task performance through cognitive strategy use.⁷ In our exploratory clinical trial for individuals with sub-acute stroke (n=26) we compared ten, 45-minute sessions of MCST (CO-OP) with dose-matched outpatient usual care outpatient occupational therapy (OT).^{7,8} The MCST (CO-OP) group demonstrated a large effect over usual care on objective measures of trained functional activities ($d=1.6$) and untrained functional activities ($d = 1.1$).⁷ The MCST group also demonstrated a moderate effect over usual care outpatient OT on improving motor function ($r = 0.3$).⁸

4. Study Procedures

- a. Study design, including the sequence and timing of study procedures (distinguish research procedures from those that are part of routine care).
- b. Study duration and number of study visits required of research participants.
- c. Blinding, including justification for blinding or not blinding the trial, if applicable.
- d. Justification of why participants will not receive routine care or will have current therapy stopped.
- e. Justification for inclusion of a placebo or non-treatment group.
- f. Definition of treatment failure or participant removal criteria.
- g. Description of what happens to participants receiving therapy when study ends or if a participant's participation in the study ends prematurely.

a. We will use a single-blind, parallel, randomized clinical trial design. The raters who will complete all the outcome assessments will be blinded. Participants will be asked prescreening questions over the phone to determine eligibility. Following baseline testing (T1), subjects will be randomized to either receive ten 45 minute sessions of metacognitive-strategy training (the Cognitive Orientation to daily Occupational Performance approach) (CO-OP) or dose-matched usual care outpatient occupational therapy. Each group will receive a total of ten 45-minute

treatment sessions, once a week. After completion of 10 intervention sessions, subjects will complete a post-intervention assessment (T2). A follow-up assessment will be conducted at three months post-intervention assessment (T3).

Name	Time Frame	Brief Description

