Stroke Impact Scale (SIS)	T1, T2, T3	The SIS is a self-report measure of stroke recovery. Specifically, the measure assesses physical, cognitive, psychosocial, community mobility, and general activity performance on a 5 point Likert scale. There is an additional item for overall recovery rated on a scale of 0 (no recovery) to 100 (full recovery).
Life Space Questionnaire	T1, T2, T3	Self-reported measure of community mobility and social participation. It is comprised of 9 yes/no questions related to places visited in the previous three days. Total score will be used in analysis.

b. Involvement in this study will consist of 3 assessment visits and 10 treatment visits, one treatment per week. The study will last for approximately 24 weeks with a total time commitment between 13-14 hours as follows:

- baseline assessment (2 hours),
- CO-OP (ten, 45 minute sessions) or
- usual care outpatient occupational therapy (ten, 45 minute sessions),
- post-intervention assessment (2 hours), and
- follow-up assessment (2 hours).

c. All raters who complete outcome assessments will be blinded to prevent biased assessment of outcomes. It is impractical to blind treating therapists, participants, and key personnel for a behavioral study of this nature.

d. This study does not request individuals to stop their routine care or current therapy. However, if a person is actively receiving rehabilitation for their upper extremity, they are not eligible to participate in this study as to avoid compromising the outcome measurement results.

e. It is important to include a usual care Occupation therapy group, so as to evaluate if MCST is more effective at improving activity performance and reducing motor impairment.

f. Participants will be removed from the study if they fail to meet to eligibility criteria or if the participant fails to attend one assessment or two treatment visits and research staff are not able to reach the participant after several attempts.

g. Participation in this study will not affect the participant's health care in any way, regardless if their participation in the study ends prematurely.

5. Inclusion/Exclusion Criteria

Inclusion Criteria:

- less than 6 months post-stroke
- adults age 50-85
- completed inpatient rehabilitation services (if recommended)
- living in the community with or without caregiver support (i.e., not living in a skilled nursing facility)
 - ability to read, write, and speak English

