 - self-identified activity performance goals per the Canadian Occupational Performance Measure (COPM)
 - upper extremity hemiparesis as indicated by a score of 1-3 on the NIHSS motor arm score

Exclusion Criteria:

- inability to provide informed consent
- severe depressive symptoms as indicated by a score >21 on the Patient Health Questionnaire (PHQ-9)
 - dementia symptoms as indicated by a score of <23 on the Montreal Cognitive Assessment (MoCA)
 - additional neurological diagnoses identified by medical chart review (e.g., brain malignancy)
 - moderate or severe aphasia as indicated by a National Institutes of Health Stroke Scale (NIHSS) aphasia score of 2 or higher
 - no voluntary movement in affected upper extremity as indicated by a score of 4 on the NIHSS motor arm score
 - anosognosia as indicated by an inability to identify activity performance problems on the COPM or PQRS
 - any other condition not otherwise specified that the PI determines would render participation in this study as unsafe
 - currently receiving outpatient rehabilitation for their upper extremity

6. Drugs/ Substances/ Devices

N/A

7. Study Analysis Plan

- a. Primary outcome variable.
- b. Secondary outcome variables.
- c. Statistical plan including sample size justification and interim data analysis.
- d. Early stopping rules.

a. The primary outcome variables will be the COPM, PQRS, and Upper Extremity Fugl-Meyer.
b. The secondary outcome variables will be the NIH Toolbox, PHQ-9, MoCA, SIS, and Life Space Questionnaire.

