c. All data will be cleaned and checked for accuracy. Data accuracy will be evaluated using a double-data entry procedure (see *Data Safety and Monitoring Plan*). As a randomized design we expect the treatment groups to be well balanced. There is always the potential for differential attrition to result in treatment groups that are somewhat imbalanced with respect to potential covariates predictive of the outcomes (see Table 3). Prior to the initial analysis we will examine differences in potential covariates and those that exhibit statistically significant and clinically meaningful differences between groups will be included as covariates in the analysis. The primary analysis for Aims 1 & 2 will be a two-factor (Group, Time) analysis of variance (or covariance) with time the repeated factor. Following a statistically significant time by group interaction effect, contrasts will be constructed to test for group differences by time point and estimate within-group change from baseline at each time point. Estimation will be via maximum likelihood methods that do not require complete data for each participant but do assume the drop out mechanism is non-informative. The primary analysis follows the intention-to-treat principal, but should the groups differ with respect to drop-out or compliance we will treat "dose" as a covariate for a secondary analysis of each aim.

d. This study will be stopped prior to its completion if: (1) the intervention is associated with adverse effects that call into question the safety of the intervention; (2) difficulty in study recruitment or retention will significantly impact the ability to evaluate the study endpoints; (3) any new information becomes available during the trial that necessitates stopping the trial; or (4) other situations occur that might warrant stopping the trial.

8. Risks

There are no expected risks from participation in this study. This expectation is based on the nature of the behavioral study but also on substantial preliminary data across three clinical trials the PI has conducted investigating this specific intervention and/or similar behavioral interventions. The risks associated with participation in this study are no greater than what the subjects may encounter in everyday life. The following risks are considered rare possible risks from participation in this study.

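### No planned analysis departs from the non-informative drop-out assumption, dose adjustment cannot test it, and Section 4f does not say that T2 and T3 are still sought after removal

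*Combined protocol and SAP*

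**What the plan says.** Under Section 4a, "Following baseline testing (T1), subjects will be randomized to either receive ten 45 minute sessions" of either intervention. Sessions are weekly, T2 follows the tenth session and T3 comes three months after T2. Section 4b puts the whole study at about 24 weeks.

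Section 4f gives one status, removal from the study. Apart from ineligibility, it applies "if the participant fails to attend one assessment or two treatment visits and research staff are not able to reach the participant after several attempts". Randomisation follows T1, so the rule reaches randomised participants. Section 4g covers only their health care after an early exit.

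Section 7c plans a Group by Time model estimated by "maximum likelihood methods that do not require complete data for each participant", and states that this assumes non-informative drop-out. It foresees differential attrition and responds in two ways. Potential covariates are compared between groups, and "those that exhibit statistically significant and clinically meaningful differences between groups will be included as covariates in the analysis". If the groups differ in drop-out or compliance, dose is added as a covariate in a secondary analysis of each aim. The primary analysis is declared intention-to-treat. Section 12 has adherence reviewed quarterly and reasons for drop-out reported annually.

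**The concern.** The likelihood analysis is sound if, given the observed scores and covariates, leaving says nothing about the unseen scores. That cannot be verified from the observed data, so the usual protection is an analysis that lets the missing scores be worse than predicted. The plan has none. Both planned responses add covariates and then rely on the same assumption. Dose is also partly a consequence of allocation, so a group contrast adjusted for it is no longer the effect of being randomised to the metacognitive strategy training (MCST) arm.

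Unequal, outcome-related loss is plausible here. Participants and therapists are unblinded, and participants are within six months of stroke, when recovery after T1 may vary widely. If the arms lose different kinds of people, the reader cannot tell whether a positive result depends on the assumption. Section 4f adds to this because the T2 and T3 scores that would help are not clearly sought once someone is removed.

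**Working it through.** **Text check.** Someone who attends weeks 1-2 and then drops out of contact could be removed about 10 - 2 = 8 weeks before T2, and about 8 + 13 = 21 weeks (five months) before T3. No section says T2 or T3 is attempted after removal, and the intention-to-treat sentence does not cover outcome collection.

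**Inputs.** From the plan: 108 participants, three time points, likelihood estimation. Assumed, because the plan gives no allocation ratio, alpha, power, attrition rate or correlations:
- 54 per arm, two-sided 5%, no true effect;
- outcome SD 1, and correlation 0.6 of T1 with T2 and with T3;
- an unmeasured prognostic factor with loading 0.6, acting on T1-T3 (stable case) or on T2-T3 only (recovery case);
- loss of both T2 and T3 when latent attendance, correlated a = 0.5 or 0.8 with the factor, falls below an arm-specific cut-off.

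Unseen T2 scores of those lost are then about 0.5-0.9 SD below those retained. With more loss in the MCST arm, the bias favours MCST.

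**Scale.** Detectable single-time difference: (1.960 + 0.842) × √(2/54) = 0.539 SD. The variance of change is 2(1 - 0.6) = 0.8, so for change it is 0.539 × √0.8 = 0.482 SD.

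**Closed form for the T2-T1 bias.** 0.6 × [a1·φ(c1)/(1 - p1) - a0·φ(c0)/(1 - p0)], where p is the proportion lost and c its normal quantile. In the stable case multiply by 1 - 0.6 = 0.4, because the T1 score already carries part of the factor. φ(c)/(1 - p) is 0.195, 0.274, 0.350 and 0.497 at 10%, 15%, 20% and 30%.
- 20% v 10%, recovery: 0.6 × 0.5 × 0.155 = 0.046 and 0.6 × 0.8 × 0.155 = 0.074; stable: 0.019 and 0.030.
- 30% v 10%, recovery: 0.6 × 0.5 × 0.302 = 0.091 and 0.6 × 0.8 × 0.302 = 0.145; stable: 0.036 and 0.058.
- 15% v 15%, same a in both arms: 0.
- 15% v 15%, a = 0.8 in one arm and 0 in the other: 0.6 × 0.8 × 0.274 = 0.132 (recovery), 0.053 (stable). With 0.8 v 0.5: 0.049 and 0.020.

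**Simulation of the planned model** (4,000 trials per scenario, Monte Carlo SE about 0.003). Bias is 0.018-0.077 SD at 20% v 10% and 0.040-0.151 SD at 30% v 10%. The upper ends are 0.077/0.482 = 16% and 0.151/0.482 = 31% of the detectable change. The Group by Time test rejects in 0.057-0.061 of trials at 15% v 15% (same mechanism), 0.068-0.078 at 20% v 10% and 0.071-0.117 at 30% v 10%.

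**Adding dose to the same trials** (time-constant, with assumed attendance patterns). In the stable case the change bias goes to about 0 (-0.003 to 0.004). In the recovery case it stays at 0.043-0.072 SD and 0.085-0.146 SD. The missing scores are what would tell the two cases apart.

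**A second mechanism.** MCST drop-out depends on the unseen T2 score; loss is about 10% in usual care and 19-24% in MCST; T2 is analysed adjusted for baseline.

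| Follow-up | Without dose | With dose |
|---|---|---|
| Stops at drop-out | 0.107, 0.215 | 0.107, 0.215 |
| Continues for all | -0.001, 0.006 | 0.027, 0.076 |

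When drop-out did not depend on the outcome (10% v 17% lost), the bias was -0.001: unequal loss alone is not the problem.

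**What a delta analysis would show.** A delta common to both arms shifts the contrast by (p1 - p0) × delta. For 0.25-1.0 SD that is 0.025-0.10 SD at 20% v 10% and 0.05-0.20 SD at 30% v 10%. Applied to the MCST arm only, the shift is p1 × delta: 0.05-0.20 SD and 0.075-0.30 SD.

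**The case against.** The strongest reply concerns Section 4f. Read as above, removal needs both missed visits and failed contact, so someone who skips sessions but answers the telephone is not removed. The clause mostly describes people already lost. That stands. A reader might infer that Section 4f itself causes the bias shown above; the documents do not support this. Those figures describe informative drop-out in general, and nothing indicates how many people could be reached again.

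A reader might also infer that non-completers have no possible T2 or T3 date. That goes too far: ten weekly sessions, a three-month interval and about 24 weeks in total let the calendar be inferred. Only an explicit rule for them is absent. Nor does the point rest on the eligibility clause ("Participants will be removed from the study if they fail to meet to eligibility criteria"), which may refer to screening only.

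In defence of Section 7c, dose adjustment is labelled secondary, also serves compliance, and leaves the intention-to-treat analysis primary. With complete data, a time-constant dose covariate does not alter the Group by Time interaction. Likelihood estimation keeps scores collected before removal. The Abstract and the Section 4 table name prognostic covariates, and Section 10 pays for each assessment. These are real mitigations. If half of those lost had already given T2, the T2-T1 bias falls to 0.006-0.033 SD (20% v 10%) and 0.015-0.060 SD (30% v 10%). A baseline covariate correlated 0.6 with the factor lowers it only to 0.013-0.072 SD and 0.029-0.141 SD. None of them tests the assumption.

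**Conclusion.** The point holds as a gap in robustness. The plan states an untestable assumption, foresees that it may be strained, and offers as its only added analysis a model that shares it. Section 4f and the intention-to-treat statement also need reconciling on whether outcomes are sought after removal.

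The likely effect is small to moderate: about 0.02-0.08 SD at 20% v 10% loss and 0.04-0.15 SD at 30% v 10%, against 0.48 SD detectable, with a rise of roughly one to two percentage points in interaction rejection in the milder case. Every input is assumed, so these figures give direction and order of size only. Two tempting readings should be resisted. Equal drop-out is not reassuring in itself: the bias is about 0 only if the mechanism is the same in both arms, and at 15% v 15% with different mechanisms it was 0.02-0.13 SD. Nor do the documents show that the primary analysis is invalid; it stands.

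**What to change.** 1. In Section 7c, pre-specify a delta-adjusted (tipping-point) sensitivity analysis of missing T2 and T3 scores for the COPM, PQRS and Upper Extremity Fugl-Meyer. Run it whether or not drop-out differs between arms. Vary delta separately by arm, for example from 0 to -1 SD in steps of 0.25 SD, and report where the conclusion changes. Do not use dose adjustment as the response to drop-out. If it is kept for compliance, define dose and label the model exploratory.
2. In Section 4f, state that missed sessions or a lapse in contact do not by themselves end outcome follow-up. T2 and T3 are still attempted on the planned calendar unless consent is withdrawn or an assessment is judged unsafe. The sponsor sets the dates for non-completers, consistent with ten weekly sessions and about 24 weeks in total. When treatment sessions stop is also left to the sponsor.

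Cost: protocol wording, some extra contact attempts by existing staff, and one sensitivity analysis for each of the three primary outcomes. The Section 4f wording is the more urgent, because outcomes never sought may not be recoverable later. This is a cheap improvement.

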Date: 06/25/2019

Version Number: 1

Principal Investigator: [name], OTD, PhD, OTR/L

Application Number: 2015868

Application Title: Efficacy of Metacognitive-Strategy Training to Improve Activity Performance and Reduce Motor Impairment in Sub-Acute Stroke

Protocol

1. Abstract

The long-term goal of this research is to improve activity performance and reduce motor impairment in individuals with stroke. There are two primary gaps in current stroke rehabilitation practice that must be addressed to achieve this goal: (1) current impairment-based approaches (e.g. motor) are not improving meaningful activity performance; and (2) current stroke rehabilitation interventions are often not designed to be clinically feasible and are rarely implemented into practice. The overall hypothesis of this proposal is that a clinically-feasible, activity-based intervention, metacognitive strategy training (MCST), will produce a significant improvement on objective and subjective measures of activity performance and motor function in comparison to a usual care occupational therapy (OT) group. These gains will transfer and generalize to untrained tasks in novel environments. The specific aims of this project are: (1) to evaluate the efficacy of MCST to improve subjective and objective activity performance in individuals with subacute stroke; and (2) to evaluate the efficacy of MCST to improve motor function in individuals with subacute stroke. Participants with subacute stroke living in the community with self-identified activity performance goals and hemiparesis will be recruited through a local stroke registry ($n = 108$). Those individuals who meet inclusion and exclusion criteria will be randomized to either a MCST group or to a usual care occupational therapy group. Both groups will receive ten, 45 minute sessions of treatment. Treatment outcomes will be assessed baseline, post-intervention, and at three-months post-intervention. Treatment efficacy outcomes will be analyzed with an intent-to-treat model with an analysis of covariance (ANCOVA). Potential covariates will include age, stroke severity, degree of cognitive impairment, and degree of motor impairment. Independent samples t-test and chi-square test will be used to ensure successful randomization and balance between groups. Group differences at baseline that are statistically significant will also be considered as covariates in the analysis. Post-hoc tests will be employed as appropriate. Significance levels, effect sizes, and confidence intervals will be reported. Completion of this study is likely to result in an efficacious, clinically feasible intervention to improve activity performance and reduce motor deficits in individuals with stroke that can be feasibly implemented into current systems of care. The proposed study and anticipated outcomes are consistent with the research priority of the National Center for Medical Rehabilitation Research (NCMRR), which is to focus on identifying, preventing, and treating key secondary conditions that are associated with physical impairments and disabilities, including stroke.

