Canadian Occupational Performance Measure (COPM)	T1, T2, T3	The COPM is a semi-structured interview guide for establishing a subject's activity performance levels within self-care, leisure, and productivity. The subject will set a minimum of 5 activity goals, providing a self-rating of 1-10
Performance Quality Rating Scale (PQRS)	T1, T2, T3	The PQRS is an observational, objective method of scoring subject activity performance of goals set via the COPM. A blind, trained rater external to the research study team will view video recordings of each subject performing goals. Each goal is rated on a scale of 1 (no activity criteria were met) to 10 (all activity criteria were met). The final score will be an average of all 5 goals.
National Institutes of Health (NIH) Toolbox Cognition Battery	T1, T2, T3	The NIHTB-CB is a collection of 7 computer-based measures assessing episodic memory, executive function and attention, working memory, language, and processing speed. As a whole, the NIH-CB is a brief assessment of fluid intelligence including problem-solving, judgment, thinking, and memory. In the present study, the fluid cognition composite T-score representing executive function will be used as an outcome measure.
Upper Extremity Fugl-Meyer	T1, T2, T3	The Fugl-Meyer is a well-established measure of upper extremity motor performance in individuals with post-stroke hemiparesis. Each item is scored either a 0 (cannot perform), 1 (performs partially), or 2 (performs fully) with a maximum score of 66.

		In the present study, the upper extremity scaled scored will be utilized.
Patient Health Questionnaire (PHQ-9)	T1, T2, T3	The PHQ-9 is a self-report measure of depressive symptoms. The subject identifies how often over the previous 2 weeks they have experienced 9 depressive symptoms. The total score reflects the severity of depressive symptoms. A score of 21 or greater indicates severe depressive symptoms. This variable will be treated as a covariate.
Montreal Cognitive Assessment (MoCA)	T1	The MoCA is a brief screener for dementia symptoms. Sixteen items are used to assess short-term memory, language, orientation, and visuospatial abilities. Within the present study, a previously established cut-off score of <23 will be indicative of cognitive impairment.

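### Time since stroke is not among the named covariates, and the visible rule for other baseline variables is a between-group significance test, so precision is lost and chance imbalance usually stays uncorrected

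*Combined protocol and SAP*

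**What the plan says.** **Eligibility (section 5).** The only explicit limit on timing is "less than 6 months post-stroke". Two other criteria act on it indirectly: "completed inpatient rehabilitation services (if recommended", which does not bind someone for whom such rehabilitation was not recommended, and "living in the community with or without caregiver support". Neither sets a minimum.

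**Design (section 4a).** Randomization follows T1, and no stratification factor is described. T2 follows ten weekly sessions, and T3 comes three months after T2.

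**Covariates.** Three places give three rules:

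- Abstract: "Potential covariates will include age, stroke severity, degree of cognitive impairment, and degree of motor impairment". It then adds "Group differences at baseline that are statistically significant will also be considered as covariates in the analysis".
- Outcome table in section 4, PHQ-9 row: "This variable will be treated as a covariate", with no test attached.
- Section 7c: groups may become "imbalanced with respect to potential covariates predictive of the outcomes (see Table 3"), and "those that exhibit statistically significant and clinically meaningful differences between groups will be included as covariates in the analysis".

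Time since stroke is not named in any of these places. Table 3 does not appear in the text available.

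**Primary model (section 7c).** A Group by Time repeated-measures analysis fitted by maximum likelihood.

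**The concern.** The change expected without any treatment effect plausibly depends on how recent the stroke was. If so, time since stroke explains part of the spread in change on the Fugl-Meyer, PQRS and COPM, and a model that leaves it out carries that spread as noise.

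The selection rule does not solve this. A baseline covariate earns its place by predicting the outcome. Section 7c describes its candidates as predictive, but then chooses among them by whether the arms differ. In a randomized trial a significant difference is a chance event, equally likely for a strong predictor and a useless one. The primary model also remains unknown until the data have been examined. At stake are the width of the confidence intervals, some power, and how well the estimate allows for whatever imbalance occurs.

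**Working it through.** **Inputs.** Total 108 (Abstract). The allocation ratio is not stated; 1:1 is assumed, giving 54 per arm. No alpha, power, design effect or dropout accompanies the 108, so it cannot be reproduced from stated inputs. The pilot motor effect r = 0.3 (section 3), converted by d = 2r/√(1 − r²) = 0.6/√0.91 = 0.63, gives 54 per arm at two-sided 5% and 90% power, but many other combinations come close, so this does not identify the design basis. Two-sided 5% is assumed below. Rho is the assumed correlation of time since stroke with the change score, given the other model terms.

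**1. How often the rule acts.** A two-sided 5% test on a randomized baseline variable is significant about 5% of the time, so about 95% of randomizations leave it out. In the simulation of step 4 it was significant in 4.7% to 5.5% of trials. The added demand for clinical meaningfulness can only lower that rate.

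**2. What imbalance escapes.** SE of the standardized baseline difference = √(2/54) = 0.192. Threshold = 1.96 × 0.192 = 0.377 SD.

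- Uniform over 0 to 6 months: SD = 6/√12 = 1.73 months; 0.377 × 1.73 = 0.65 month, about 20 days.
- Uniform over a 3-month range: SD = 0.87 month; 0.377 × 0.87 = 0.33 month, about 10 days.

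Shift in the treatment contrast = rho × standardized imbalance. For rho 0.1, 0.3 and 0.5:

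- just under the threshold: 0.04, 0.11 and 0.19 SD;
- at an imbalance of one SE: 0.02, 0.06 and 0.10 SD.

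**3. Precision from always adjusting.** Adjusted variance = (1 − rho²) × unadjusted variance. The effect giving 80% power unadjusted is d = (1.960 + 0.842) × 0.192 = 0.539. Adjusted power = Φ(0.539/(0.192 × √(1 − rho²)) − 1.96). The total giving the same power as 108 unadjusted is 108 × (1 − rho²).

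| rho | Power at d = 0.539 | Equivalent total | Power at d = 0.63 |
|---|---|---|---|
| none (unadjusted) | 80.0% | 108 | 90.5% |
| 0.1 | 80.4% | 107 | 90.7% |
| 0.2 | 81.6% | 104 | 91.6% |
| 0.3 | 83.5% | 98 | 92.9% |
| 0.4 | 86.3% | 91 | 94.6% |
| 0.5 | 89.9% | 81 | 96.5% |

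**4. What the significance rule recovers.** Simulation of 6,000 trials per setting: one change-type outcome, time since stroke uniform over 0 to 6 months, d = 0.539, significance part of the rule only.

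| rho | Never adjust | Adjust if p < 0.05 | Always adjust |
|---|---|---|---|
| 0.2 | 78.6% | 78.7% | 80.0% |
| 0.3 | 79.0% | 79.3% | 82.5% |
| 0.5 | 77.6% | 78.8% | 88.3% |

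Monte Carlo error is about √(0.8 × 0.2/6000) = 0.5 point, so compare within rows. The rule recovers about 0.1 of 1.4 points, 0.3 of 3.5 and 1.2 of 10.7. Type I error was 4.5% to 5.3% and mean estimates were unbiased under all three strategies.

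**5. How the covariate must enter.** With T1 among the responses, the Group by Time contrast compares within-person changes. A covariate effect that is constant over time cancels from a change, so a main effect alone leaves the contrast essentially as it was. The interaction with Time is what removes differences in recovery slope.

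**The case against.** **Table 3 may list it.** A reader might infer that time since stroke is definitely not a candidate covariate. The documents do not support that: Table 3 is cited but not available, and the Abstract's list need not be exhaustive. This limits the claim about omission, but not the objection to the rule, because section 7c would still require a group difference before using it.

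**The rule is not uniformly test-only.** In the Abstract, the word *also* suggests that the named covariates need no test, and the PHQ-9 enters without one. This is fair. The three places disagree, and the disagreement itself needs resolving. Time since stroke benefits from neither exception.

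**Randomization protects validity.** A reader might infer a biased estimate or an inflated false-positive rate. Neither follows: assignment is random, unadjusted standard errors already allow for chance imbalance, and the simulation shows both properties intact. The shifts in step 2 are conditional on a given imbalance, and those just under the threshold are close to the worst that can escape.

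**Entry close to onset may be rare.** The rehabilitation and community-living criteria raise the realised minimum for many participants. The full 0 to 6 month spread is what the criteria permit, not what will necessarily be enrolled, hence the 10-day figure beside the 20-day one.

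**The gain may be small.** The repeated-measures model already removes stable differences between people, and severity and motor covariates may absorb part of the rest. A correlation that matters for the Fugl-Meyer need not hold for self-rated COPM goals. The pilot effects for activity performance were d = 1.6 and 1.1; at d = 1.1, power with 54 per arm is already near 100%. A reader might infer a large rescue of power, but that needs both a high rho and an effect well below the pilot values, and the documents establish neither.

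**Conclusion.** The point holds as a modest, inexpensive improvement in efficiency and prespecification. No minimum time since stroke is stated, the variable is not named as a covariate in the text available, and section 7c's rule would leave it unadjusted in about 95% of randomizations.

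The cost is precision, plus chance imbalance that goes uncorrected. Against 80% unadjusted power, always adjusting gains 0.4 to 3.5 points for rho of 0.1 to 0.3, and 9.9 points at rho 0.5. These figures rest on 1:1 allocation, two-sided 5%, complete data and an assumed rho, so they are a range and not a corrected figure for this trial. The mismatch between the Abstract, the outcome table and section 7c stands whatever rho is.

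**What to change.** - In section 7c, and consistently in the Abstract, replace the baseline-significance rule with a fixed covariate set chosen for prognostic value: the covariates already named (age, stroke severity, cognitive impairment, motor impairment, PHQ-9) plus days since stroke at T1.
- Enter days since stroke with its interaction with Time in the COPM, PQRS and Fugl-Meyer models, regardless of any baseline test.
- State how the T1 outcome is used. Either keep it as a response in the repeated-measures model, or use it as a covariate with only T2 and T3 as responses, but not both.
- Check whether Table 3 lists time since stroke, and bring it into line with the fixed set.

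**Cost.** A few sentences. Timing of the stroke is already needed to apply the eligibility limit, so no new assessment is required. Days since stroke uses three degrees of freedom with T1, T2 and T3 as responses (one main effect, two interaction terms), or two if only T2 and T3 are responses.
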